15.2.3. Data Protection & Patient Confidentiality

All investigators and trial site staff involved in this trial will comply with the requirements of the Data Protection Act 1998 with regards to the collection, storage, processing and disclosure of personal information.

The trial staff will ensure that the participants' anonymity is maintained. The participants will be identified by initials, DOB and a participant ID number on the CRF and Trial Management System Database. Consent forms will contain participant names. All documents will be stored securely and only accessible by trial staff and authorised personnel.

16. Withdrawals

The main ground for withdrawal from the trial is participant request. Participants may request this at any time. It is anticipated that the research team will seek to understand the participant's barriers to further trial participation and to address these where possible. In this instance, the researcher should ascertain whether the participant is still willing to undergo follow up, and if possible document the reason for withdrawal.

Participants also may be withdrawn if the study sponsor or regulatory authorities terminate the study prior to its planned end date.

17. Serious Adverse Events (SAEs)

It is not anticipated that the intervention sessions will result in any serious adverse events. However, each PI will report all SAEs not listed below to the CI within 24 hours of first notification. The Chief Investigator is responsible for ensuring the assessment of all SAEs for expectedness and relatedness is completed and the onward notification of all non-exempt SAEs to the Sponsor immediately but not more than 24 hours after first notification.

- Cardiovascular (CV) death e.g. fatal myocardial infarction [MI] / cerebrovascular accident [CVA] / congestive heart failure [CHF] / arrhythmia, cardiac arrest, death following CV intervention
- Non-fatal stroke/TIA
- Non-fatal MI
- Acute coronary syndrome
- CHF requiring hospitalisation
- Unstable angina requiring hospitalisation
- Any hospitalisation due to cardiovascular events
- Hospitalisation for any elective/pre-planned surgical procedure for pre-existing condition prior to trial enrolment
- Atrial fibrillation/Atrial flutter
- Ventricular fibrillation/tachycardia requiring intervention
- Deep Vein Thrombosis (DVT)
- Pulmonary embolism
- Percutaneous Coronary Intervention (PCI) (including non-serious events)
- Accelerated or malignant hypertension/hypertensive urgency

The sponsor will keep detailed records of all SAEs reported to them by the trial team.

18. Ethical Considerations

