9.2. Follow-up Data Collection

Follow-up via postal questionnaire will take place at six months after entry into the trial. These will include all of the baseline instruments. Non-responders will be followed up by telephone.

Follow-up at twelve months will comprise a combination of postal and telephone administered questionnaires including all of the baseline instruments plus the Southampton Stroke Self-management questionnaire (SSSQ) and the Health Literacy Questionnaire (HLQ). Non-responders to the postal questionnaires will be

followed up by telephone. Again, where a patient has difficulty completing a questionnaire because of physical or communication difficulties, they will be encouraged to seek the help of a carer.

A review of general practice notes will also be conducted. Data extracted will include number and nature of primary care visits, secondary care inpatient and outpatient visits, investigations, medications and use of social services.

10. Statistical Methods and Analysis

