To explore uncertainties in the analyses, deterministic sensitivity analysis is proposed to test the robustness of the results when varying key assumptions (for example, length of time required to deliver the intervention). Probabilistic sensitivity analysis will be undertaken to incorporate the uncertainty around parameter values and quantify the overall decision uncertainty, with results presented as cost-effectiveness planes and cost-effectiveness acceptability curves.

11. Intervention fidelity

There will be both quantitative and qualitative assessment of the extent to which the intervention is implemented as planned. Our general approach to fidelity assurance is to use both real time practice data and real time informal feedback from the practice staff from regular telephone conversations, with visits where appropriate. These regular contacts will enable us to devise shared solutions to any fidelity issues.

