11.1. Structured Review of Patient Needs

We will capture data relating to completion of the review checklist, development of action plans, and resolution of problems. A random sample (up to 10%) of the reviews will be audio-taped and assessed for fidelity. We will also ascertain whether the checklist continues to be used at the end of follow up (i.e. at twelve months).

We will regularly review the process and clinical data, and feedback to practice staff either in person or by telephone. We will ask practice staff whether they have encountered problems implementing the review service, and discuss the reasons for this (e.g. operational issues, staff capacity). Where implementation and intervention fidelity are a concern, we will ask the practice staff to reflect upon the specific actions or processes, and through negotiation develop a joint action plan to address these issues. This "real-time" feedback to practice staff will ensure that the model of care is delivered consistently in accordance with the implementation plan across the duration of the practice involvement.

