11.5. Service Mapping

This will be monitored through the regular feedback sessions with practice staff. We will look at how often the data is referred to, is it easy to access, whether the service being recommended was appropriate for the patient, and whether the service data is comprehensive i.e. does it contain all relevant sources or are there significant omissions.

If necessary, we will amend the format to allow easier access and searching of the data. Where significant omissions are found we will update our search to include new services.

12. Process evaluation

In both intervention and control practices, we will capture process data from the GP records to count the number of consultations, sub-divided into those related to stroke and those unrelated to stroke, and whether the consultation was with GP or practice nurse; prescriptions; and the number of referrals to secondary care. We will collect data on the background/speciality of the nurses performing reviews and of the facilitators conducting the MLAS courses, and how the direct point of contact was operationalised within each practice. Patient questionnaire at follow up will assess contact with other local services. To enable comparison of process between intervention and control practices, a sample of up to 10% of annual reviews in the control practices will be audiotaped. We will carry out semi-structured interviews with participants to explore experience of stroke care over the period of the study. We will also carry out semi-structured interviews with primary care professionals to explore attitudes to and experience of communication with specialists and confidence with

using referral pathways; reflections on the annual review; awareness of local services; strengths and weaknesses of current stroke services in the community.

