# 4.2 Purpose of the analyses

These analyses will assess the efficacy and safety of a novel model of primary care for stroke survivors living in the community compared to standard care. A health economic analysis plan (HEAP) will be documented separately.

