#### 6.5 Study Variables

The frequency and timing of the main variable assessments is outlined in the Table 1. The primary outcome data will be collected via postal questionnaire at the time of invite to the study prior to Practice randomisation. Secondary outcome data (SIS Short Form, EuroQol EQ-5D-5L, and ICEpop CAPability measure for Adults (ICECAP-A)) will also be collected by postal questionnaire after randomisation. Non-responders to the secondary outcome questionnaire will be followed-up by telephone.

Follow-up via postal questionnaire will take place at six months after entry into the trial. These will include all of the baseline instruments. Non-responders will be followed up by telephone.

Follow-up at twelve months will comprise a combination of postal and telephone administered questionnaires including all of the baseline instruments plus the Southampton Stroke Self-

management questionnaire (SSSMQ) and the Health Literacy Questionnaire (HLQ). Non-responders to the postal questionnaires will be followed up by telephone.

Study assessment	Throughout	Baseline	6 months	12 months
Demographics (age, gender, etc)		х		
SIS short-form questionnaire		x	x	х
SIS full-form (emotional and handicap		х	х	х
domains only) questionnaire				
EQ-5D-5L questionnaire		х	x	х
ICECAP-A questionnaire		х	x	х
Health Literacy Questionnaire (HLQ)				х
Southampton Stroke Self-				х
Management Questionnaire (SSSMQ)				
SAE monitoring	х			
Review of general practice data				х
(number and nature of primary care				
visits, secondary care inpatient and				
outpatient visits, investigations,				
medications and use of social				
services, etc)				

**Table 1**: Frequency and timing of main variables and questionnaires.

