# **13** Safety Analyses

Patient-level safety data collected during the trial will be included in the reporting of safety events, from the point of patient consent to participate in the trial until the end of the follow-up period or loss to follow-up.

Coding of safety events (e.g. MedDRA) is not being utilised in the IPCAS trial.

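### SAE capture is described only as notification-driven while study-team contact is greater in the intervention arm, so reading the SAE listing by arm may partly reflect reporting

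*Protocol*

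**What the plan says.** **Capture.** Protocol section 17 requires that "each PI will report all SAEs not listed below to the CI within 24 hours of first notification", and the list that follows exempts mainly cardiovascular events. SAP Table 1 has a row for "SAE monitoring", marked only in the continuous column and not at baseline, 6 or 12 months. SAP 13 sets the window as "from the point of patient consent to participate in the trial until the end of the follow-up period or loss to follow-up".

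**Use.** SAP 4.2 says the analyses are to "assess the efficacy and safety of a novel model of primary care", set against standard care. SAP 8.2.3 defines a safety population of all consented patients. SAP 13.2 then specifies one table with a row for each event, not categorised by type, and says that all SAEs are recorded and reported. The text does not say whether that table is split by arm. The skeleton tables are in a separate file.

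**Contact.** Protocol section 11, which deals throughout with intervention components, relies on "real time informal feedback from the practice staff from regular telephone conversations, with visits where appropriate". Section 11.1 adds: "We will regularly review the process and clinical data, and feedback to practice staff either in person or by telephone".

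**Sources not limited to one arm.** On the GP notes review, Protocol 9.2 says: "Data extracted will include number and nature of primary care visits, secondary care inpatient and outpatient visits". SAP Table 1 places that review at 12 months. Protocol section 12 says: "In both intervention and control practices, we will capture process data from the GP records". SAP 9.1 lists death among the reasons for a missed visit, loss to follow-up or withdrawal. SAP 13 draws on none of these.

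**The concern.** If an SAE enters the dataset mainly because somebody tells the study team, the chance of entry depends on how often the team and the practice talk. Here that frequency differs by arm as a result of the design. The likely direction is more reported SAEs in the intervention arm, although the documents cannot confirm it.

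The listing is the only specified safety output, so anyone who wants to judge safety against standard care has to count its rows by arm. That includes the combined TSC/DMC, whose remit covers the safety profile. An apparent excess in the intervention arm could be reporting, and a true excess in the control arm could be hidden. The plan carries no warning of this.

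**Working it through.** **Step 1. Contact routes side by side**

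| Route to the study team | Intervention | Control |
|---|---|---|
| Regular calls, visits where needed (Protocol 11) | Yes | Not described |
| Recurring review of process and clinical data with feedback (Protocol 11.1) | Yes | Not described |
| Feedback sessions and specialist-contact logs (Protocol 11.3 to 11.5) | Yes | Not described |
| MLAS sessions, opt-in (Protocol 7.1.2, 18.3) | Up to 1 + 4 + 1 = 6 | None |
| Audiotaped reviews (Protocol 11.1, 12) | Up to 10% | Up to 10% |
| Description of usual care (SAP 9.1) | Not applicable | Yes |
| End-of-study interviews (Protocol 12.1, 12.2) | 15 patients, 10 staff | 10 patients, up to 5 staff |
| 6- and 12-month questionnaires, telephone follow-up of non-responders (Protocol 9.2) | Yes | Yes |
| GP notes review (Protocol 9.2, SAP Table 1) | Yes | Yes |

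The recurring contacts with practice staff are all on the intervention side. The last two routes are common to both arms, but the plan does not connect either to SAE capture.

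**Step 2. Direction and size**

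The plan gives no SAE rate and no reporting probability, so there is no safety figure to reproduce. The one planned number needed is the arm size: 23 practices x 20 patients = 460 per arm, and 2 x 460 = 920, as stated.

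Let r be the true 12-month SAE risk, equal in both arms, and let q_I and q_C be the probabilities that an SAE is reported in each arm. Then

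expected reported ratio = (460 x r x q_I) / (460 x r x q_C) = q_I / q_C.

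The true risk cancels. All values of r, q_I and q_C below are assumptions:

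| True risk | Patients with an SAE per arm | Reported at 60% v 50% | Reported at 80% v 50% |
|---|---|---|---|
| 5% | 23 | 13.8 v 11.5 | 18.4 v 11.5 |
| 10% | 46 | 27.6 v 23.0 | 36.8 v 23.0 |
| 20% | 92 | 55.2 v 46.0 | 73.6 v 46.0 |
| Ratio | 1.0 | 1.2 | 1.6 |

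If the true risks differ, reported ratio = true ratio x (q_I / q_C). A true ratio of 1/1.2 = 0.83 would appear as 1.0 at 60% v 50%.

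**Step 3. Would a reader notice?**

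No test is planned, so this step only gives scale. Take a two-sided 5% test of two proportions, 460 per arm, and 10% true risk in both arms. The chance of p < 0.05 is 45% at 80% v 50% reporting and 9% at 70% v 60%, against a nominal 5%. Now assume an SAE intraclass correlation of 0.01 and use the plan's cluster-size coefficient of variation of 0.65. The design effect is 1 + ((0.65² + 1) x 20 - 1) x 0.01 = 1.27, and the chances fall to 37% and 8%.

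**The case against.** The strongest reply is that the SAP specifies no comparison by arm. SAP 13.2 plans a listing with no rate, test or denominator, and expects few events. That is correct. The point therefore concerns any comparison drawn from the listing to meet the SAP 4.2 purpose, not a prespecified test. With few events a modest gap may be invisible, but that does not make the comparison valid.

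Second, a reader might infer that SAEs count only if notified. The documents do not say so. First notification starts a reporting clock, and SAP 13 refers to safety data collected during the trial without limiting the source. Protocol 15.2.1 also provides a channel for practices to exchange SAE information with the team, in either arm. What stands against the plan is that no other route is described, not that other routes are excluded.

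Third, some features that look like causes do not themselves separate the arms. Section 17 places the duty on each PI while section 15 names only the Cambridge PI, but that ambiguity affects both arms. The structured review and the direct contact line are run by the practice and do not in themselves inform the study team. MLAS is optional, and its facilitators have no stated SAE role. The argument rests on the recurring contact between team and practice.

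Fourth, a high assumed SAE risk would sit badly with the Protocol 17 exemption list, which removes many cardiovascular events from reporting. This objection is fair, and it is why the working gives a range.

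**Conclusion.** The concern holds with the word may. SAE capture is described only as notification-driven, planned study-team contact with practices is greater in the intervention arm of an open-label trial, and the only specified safety output cannot by itself support a comparison with standard care. The bias factor is q_I / q_C: 1.2 or 1.6 on the assumed pairs above, and unknown in fact.

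A reader might go further and infer that the listing will show a difference between arms, or that no sound safety conclusion is possible. The documents support neither. They give no reporting probabilities, both arms share the questionnaires and the notes review, and the oversight committee can still assess individual events for relatedness whatever the counts by arm.

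The conclusion assumes that section 11 contact applies to intervention practices only. Its content implies this, but the protocol does not say so in terms.

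**What to change.** - In SAP 13, add a descriptive safety summary by arm: number of patients and number of events, with the safety population as denominator. Base it on inpatient admissions from the 12-month GP notes review and on recorded deaths, using the same fields and the same window in both arms.
- Keep notified SAEs as a listing that shows arm and source of report, and state that it is not used to compare arms.
- Reconcile the Protocol 17 exemption list with the SAP 13.2 statement that all SAEs are recorded and reported.

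**Cost.** The change is mainly SAP wording, because the notes review already covers the number and nature of inpatient visits and death is already recorded for patient disposition. Some re-extraction may be needed if reason for admission or date of death was not captured; the extraction form is not in the documents.

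**Downside.** The summary is available only after the notes review. It misses admissions that are absent from the GP record and SAEs that involve neither admission nor death, and notes may be incomplete for patients who left the practice. It also assumes that GP records capture admissions about equally well in the two arms.

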7.1.1. Structured Review of Patient Needs

A structured review will be performed by a Practice nurse or other appropriately trained member of the Practice team as part of the regular annual review recommended by current guidelines¹⁰. As part of the review, a 15-item checklist of post-stroke needs (see appendix A) will be sent by the Practice to the stroke survivor in advance. The survivor will be asked to tick all needs which apply to them, and to bring this with them to the appointment. At the review, the patient will be asked which of the ticked items is the most important and they would like to discuss most. Dependent upon time availability at the review, Practice staff will discuss and address up to three key needs identified by the survivor. A blank checklist will also be available in the Practice if needed.

The review will last approximately 20-30 minutes, and include a routine physical check-up based on QoF recommendations (e.g. blood pressure, record of immunisation, and medication review) followed by the discussion of up to three post-stroke needs as identified by the stroke survivor. The expected outcome of the review is an action plan agreed with the stroke survivor on how to address each of the needs identified in the review. A record of the checklist and the agreed action plan (e.g. referrals, agreed actions to be undertaken by the patient) will be kept in the patient records.

The patient will be provided with an information leaflet about the MLAS programme, with instructions on how to get further information from the MLAS team and how to access the programme.

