15.1 Monitoring

Oversight of the trial will fall to an independent committee fulfilling the combined roles of Trial Steering Committee (TSC) and Data Monitoring Committee (DMC). They will provide overall supervision of the conduct of the trial on behalf of the trial sponsor(s) in accordance with NIHR recommendations^{22,23}. The committee will consider relevant factors in interim decision-making, such as recruitment rate and completion schedule, baseline comparability across treatment arms, data completeness and follow-up, safety profile and ethical issues.

Initially, the TSC/DMC will meet after the first 100 participants are recruited, then 6monthly. This frequency may increase or decrease according to need.

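### Protocol 17 exempts 14 event categories from SAE reporting with no relatedness condition, states no route to the relatedness assessment it requires for all SAEs, and disagrees with SAP 13.2

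*Protocol*

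**What the plan says.** Protocol 17 sets out three duties in two consecutive sentences.

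- PI to CI: "each PI will report all SAEs not listed below to the CI within 24 hours of first notification".
- Assessment: "The Chief Investigator is responsible for ensuring the assessment of all SAEs for expectedness and relatedness is completed".
- CI to sponsor: "the onward notification of all non-exempt SAEs to the Sponsor immediately but not more than 24 hours after first notification".

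The list that follows has 14 entries. Most name a kind of event, and some are very broad, such as "Any hospitalisation due to cardiovascular events". One is qualified by circumstance: "Hospitalisation for any elective/pre-planned surgical procedure for pre-existing condition prior to trial enrolment". The protocol opens the section by saying that no serious adverse events are expected from the intervention sessions.

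SAP 13.2 defines an SAE in the usual way, says the trial team will record and report all of them, and plans a table with one row per event. It mentions neither the protocol's list nor a relatedness assessment. SAP 13.1 says that non-serious adverse events will not be formally recorded.

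**The concern.** An exemption list of this kind normally rests on expectedness: cardiovascular events will occur in stroke survivors whatever the trial does, and reporting each one urgently adds little. Expectedness and relatedness are separate questions, however, and the protocol asks for both. Here the exemption is applied on the nature of the event before anyone has judged cause. The PI has no instruction to report a listed event that he or she suspects was caused by the intervention, and the CI has no stated means of learning of it in order to meet the assessment duty.

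What is at stake is the handling of the uncommon case for which expedited reporting exists: a serious event that someone at the practice thinks the intervention may have caused. Because non-serious events are not recorded, SAEs are the trial's only formal adverse-event data. The disagreement with the SAP also leaves the content of the final SAE table open. It could hold all SAEs or only unlisted ones, and a reader of the trial report could not tell which.

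**Working it through.** No arithmetic applies beyond a count of the list. The check is a comparison of scope.

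**1. Scope of each duty**

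| Duty | Source | Events covered | Relatedness condition |
|---|---|---|---|
| PI reports to CI | Protocol 17 | Unlisted SAEs only | None |
| CI ensures assessment of expectedness and relatedness | Protocol 17 | All SAEs | Not applicable |
| CI notifies sponsor | Protocol 17 | Non-exempt SAEs only | None |
| Trial team records and reports; one table row per event | SAP 13.2 | All SAEs | Not mentioned |

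The second row is wider than the first, and the first is the only step that brings an event to the CI. The difference between them is the 14 listed categories.

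**2. Does any listed entry carry a causality condition?** Of the 14 entries, 13 are defined by the kind of event, some with a severity or setting qualifier such as a need for hospital admission. The remaining one (14 − 13 = 1), elective or pre-planned surgery, depends on a pre-existing condition, which is not a judgement about the intervention. Entries conditional on being unrelated: 0 of 14.

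**3. Is there another route to a relatedness assessment?**

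- Protocol 17, closing line: the sponsor keeps records of SAEs reported to it, so this adds no route for events that are not reported.
- Protocol 15.2.1: names a secure e-mail channel for reporting and assessing SAEs, but not which events go through it.
- Protocol 9.2 and SAP 6.5: the review of practice notes collects inpatient visits as resource use, with no causality step.
- SAP 6.5, Table 1: SAE monitoring runs throughout, with no statement on listed events or on cause.
- SAP 9.1: death is recorded as a reason for withdrawal, with no causality step.
- SAP 13.2: all SAEs are recorded and reported, but no recipient within the trial and no relatedness step is named.

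Stated routes by which a listed SAE reaches the CI for relatedness assessment: none.

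**4. A test case.** Suppose a participant has a cardiac event, of a kind on the list, during an MLAS group session, and the PI suspects a link. Under Protocol 17 the event is listed, so the PI owes no 24-hour report. It is exempt, so the CI owes the sponsor no notification. The CI nevertheless remains responsible for seeing that its relatedness is assessed. Under SAP 13.2 the same event is to be reported and given a row in the table.

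**The case against.** The strongest reply is that the paragraph can be read coherently. The sentence on the CI uses two different scopes, all SAEs for assessment and non-exempt SAEs for notification. If only unlisted events ever reached the CI, the second phrase would be redundant. On that reading the list waives the 24-hour report and the sponsor notification but leaves assessment in place, to be done later. This stands as an account of what was probably intended, and it is why the defect is an unstated route and not proof that listed events are never assessed. It does not repair the plan: no later step, timeline or form is described, so a practice could not follow it. Even on this reading, a listed event suspected to be related stays outside the 24-hour report and the sponsor notification.

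It can also be said that the intervention is low risk and that the list is a reasonable way to avoid noise. Both are fair. They limit the seriousness of the point, but an expectation of no harm still needs a way to detect an exception.

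Four stronger readings are tempting, and the documents do not support them.

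- A reader might infer that listed events disappear from the study team's view. SAP Table 1 and SAP 13.2 point the other way; what is missing is a causality step.
- A reader might infer that the combined TSC/DMC, which is to consider "baseline comparability across treatment arms, data completeness and follow-up, safety profile and ethical issues", would see only the events least likely to be related. Nothing limits its safety data to unlisted events. Unlisted serious events such as an injury or a mental-health crisis could well be related, and they stay on the 24-hour route.
- A reader might point to the review, which will "include a routine physical check-up based on QoF recommendations (e.g. blood pressure, record of immunisation, and medication review"), as a specific path from the intervention to cardiovascular events. Protocol 7.1.1 and 18.3 place the review within the regular annual review, and SAP 9.1 provides for QOF-related review content in control practices, so that check is largely shared with usual care.
- A reader might want a number of participants affected. The documents give no rate for any listed event. A rate applied to all 920 participants would also count the control arm, and would count listed events, not related ones.

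**Conclusion.** The point holds in this form. Protocol 17 exempts 14 categories from the PI's report with no relatedness condition (0 of 14), requires relatedness to be assessed for all SAEs, and states no route or timeline that connects the two. SAP 13.2 has no exemption, so the documents disagree on which SAEs are reported and tabulated.

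Its size is the full list of 14 categories; no participant count is justified. The conclusion rests on the wording alone, not on any assumed event rate, causal mechanism or sample-size figure. It takes exempt in the notification sentence to mean listed, which is the only sense the section offers. A separate site instruction could supply the missing step, but neither document cites one for this purpose.

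This should be corrected, but it does not threaten the co-primary analyses. The low risk of the intervention keeps it below the most serious class.

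**What to change.** In Protocol 17, keep the list and make the exemption conditional:

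1. The PI records a relatedness judgement for every SAE that comes to notice, listed or not.
2. Only a listed event judged unrelated to the intervention is exempt from 24-hour reporting.
3. A listed event judged possibly related goes by the normal route to the CI and the sponsor.
4. The protocol says how and when the recorded judgements on exempt events reach the CI, so that the assessment duty can be met.

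Then reconcile Protocol 17 with SAP 13.2 on which SAEs are reported, which are assessed for relatedness and which appear in the SAE table. If the table is to leave out exempt events, SAP 13.2 should say so.

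The cost is a few sentences in each document, one field on the event form, a judgement by the PI for each listed event noticed, and a few more expedited reports. A smaller change, stating only when listed events are assessed, would close the assessment gap but would leave a suspected related event outside 24-hour reporting.
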